# **Photoplethysmography to detect circulatory arrest: A study in patients with induced cardiac arrests**

## **- DETECT-1 -**

**(October 2023)**

### Protocol amendments:

Amendment 1 - June 2022: the maximum number of patients in whom no circulatory arrest was induced (no need for rapid ventricular pacing with aortic balloon dilatation during TAVR) that could be included was increased and it was better explained that the collected data is used as non-circulatory arrest data.

Amendment 2 - November 2022: the number of TAVR-patients to be included was increased, and number of s-ICD and VT ablation patients was decreased.

Amendment 3 – October 2023: removing extended data collection from the protocol, detailing the statistical analysis including addition of a subgroup for external validation.

**LIST OF ABBREVIATIONS AND RELEVANT DEFINITIONS**

ABR	General Assessment and Registration form (ABR form), the application form that is required for submission to the accredited Ethics Committee; in Dutch: Algemeen Beoordelings- en Registratieformulier (ABR-formulier)
AE	Adverse Event
AR	Adverse Reaction
CA	Competent Authority
CCMO	Central Committee on Research Involving Human Subjects; in Dutch: Centrale Commissie Mensgebonden Onderzoek
CCU	Coronary Care Unit
CPR	Cardiopulmonary resuscitation
CV	Curriculum Vitae
DSMB	Data Safety Monitoring Board
ECG	Electrocardiogram
ED	Emergency department
EDC	Electronic data capture
EU	European Union
EudraCT	European drug regulatory affairs Clinical Trials
GCP	Good Clinical Practice
GDPR	General Data Protection Regulation; in Dutch: Algemene Verordening Gegevensbescherming (AVG)
HIPAA	Health Insurance Portability and Accountability Act
IB	Investigator's Brochure
IC	Informed Consent
ICD	Implantable cardioverter defibrillator
ICU	Intensive care unit
IMDD	Investigational Medical Device Dossier
IMP	Investigational Medicinal Product
IMPD	Investigational Medicinal Product Dossier
ISO	International organization for standardization
LED	Light Emitting Diode

---

METC	Medical research ethics committee (MREC); in Dutch: medisch-ethische toetsingscommissie (METC)
OHCA	Out-of-hospital cardiac arrest
PPG	Photoplethysmography
ROSC	Return of spontaneous circulation
(S)AE	(Serious) Adverse Event
SPC	Summary of Product Characteristics; in Dutch: officiële productinformatie IB1-tekst
Sponsor	The sponsor is the party that commissions the organisation or performance of the research, for example a pharmaceutical company, academic hospital, scientific organisation or investigator. A party that provides funding for a study but does not commission it is not regarded as the sponsor, but referred to as a subsidising party.
SUSAR	Suspected Unexpected Serious Adverse Reaction
TAVR	Transcatheter Aortic Valve Replacement
UAVG	Dutch Act on Implementation of the General Data Protection Regulation; in Dutch: Uitvoeringswet AVG
VT	Ventricular tachycardia
VF	Ventricular fibrillation
WMO	Medical Research Involving Human Subjects Act; in Dutch: Wet Medisch-wetenschappelijk Onderzoek met Mensen

## SUMMARY

**Rationale:** Out-of-hospital cardiac arrest (OHCA) is a leading cause of global mortality. Delays to initiation of cardiopulmonary resuscitation (CPR) should be as short as possible to achieve the highest survival chance. To reduce treatment delays automated cardiac arrest detection and call for help would be ideal. Photoplethysmography (PPG) is an optical technique often used in sport/smartwatches to monitor heart rhythm at the skin and based on previous studies it seems to have potential to detect circulatory arrest.

**Objective:** To study photoplethysmography signals during 1) induced circulatory arrest; 2) cardiac rhythms without circulatory arrest, and to construct a PPG-based algorithm for circulatory arrest detection.

**Study design:** Prospective multicenter observational study.

**Study population:** 1) Patients scheduled for defibrillation testing after (subcutaneous) implantable cardioverter defibrillator (ICD) implantation; 2) Patients undergoing transcatheter aortic valve replacement (TAVR) with intended rapid ventricular pacing; 3) Patients undergoing ventricular tachycardia ablation.

**Intervention:** Patients will be equipped with a wristband with a PPG-sensor to record PPG signals during hospital stay including during induced circulatory arrests. The circulatory arrest inductions are part of routine practice during above-described procedures and are not a study-related intervention. In case this is not routine practice, an arterial line will be inserted as reference standard for circulatory arrest.

**Main study parameters/endpoints:** Primary endpoints: Sensitivity for circulatory arrest and false positive circulatory arrest alarms.. Secondary endpoints: Positive predictive value for circulatory arrest, Specificity for detection of pulsatile PPG signal, PPG-signal characteristics.

**Nature and extent of the burden and risks associated with participation, benefit and group relatedness:** Given the observational nature of this study and the non-invasive comfortable wristband used for PPG signal recording, the medical risk associated with study participation is negligible. Insertion of an arterial line may carry small risks as outlined in this protocol.

## 1. INTRODUCTION AND RATIONALE

Out-of-hospital cardiac arrest (OHCA) is a leading cause of global mortality, with 300 cases in the Netherlands each week (1). Survival to hospital discharge is about 25% and depends on fast recognition of cardiac arrest and immediate initiation of cardiopulmonary resuscitation (CPR) (1-3). Survival chance decreases with 5-10% per minute delay to defibrillation emphasizing the need to keep treatment delays as short as possible (2). The establishment of a nationwide network of lay rescuers initiating CPR prior to ambulance arrival has contributed to shortening of treatment delays and improved survival (3). Automated cardiac arrest detection and call for help would be a next important step, also enabling timely help for victims of unwitnessed cardiac arrest, constituting 25-50% of all cardiac arrest victims (1,4).

Contemporary wearable technologies may play an important role to fulfil this goal (5). The risk of sudden cardiac death increases already from the fourth decade in life, and in about half of cases cardiac arrest is the first manifestation of disease (1,6). Therefore, a tool for automated cardiac arrest detection should be widely applicable and comfortable to wear.

Photoplethysmography (PPG) is a low-cost, non-invasive optical technique using measurements at the skin to detect blood volume changes in the microvascular bed of tissue (7). It is used in pulse oximeters to provide measurements of oxygen saturation and in sport/smartwatches to monitor heart rate (5,7). Additionally, it is increasingly used in commercially available medically oriented devices to detect cardiac arrhythmias, most often focusing on detection of atrial fibrillation (5). Given its reflection of hemodynamic information, this technique may also be suitable to detect circulatory arrest (8).

A previous study in animals has shown feasibility of detection of hemodynamically unstable cardiac arrhythmias using a single derived parameter of the PPG signal (8). Additionally, high correlation was shown between changes in blood pressure and PPG output. In cardiac arrest patients, PPG is under active investigation to detect return of spontaneous circulation (ROSC) during resuscitation and seems to perform even better than manual pulse palpation (9-11). In contrast to the electrocardiogram (ECG) reflecting electrical activity of the heart, PPG provides assessment of hemodynamic status, and therefore functions more as a derivative of the mechanical activity of the heart. This is important as it enables not only detection of ventricular fibrillation and asystole, but also pulseless electrical activity, which is the initial cardiac rhythm in about 20% of cardiac arrests (12).

In the DETECT-project, we aim to further develop an existing medically oriented wristband to fulfil the goal of automated cardiac arrest detection and activation the emergency

medical chain. In the present DETECT-1 study, we will study PPG signals in relation to induced circulatory arrests and develop a PPG-based algorithm for detection of circulatory arrest.

## 2. OBJECTIVES

Primary Objectives:

- 1) To study PPG signal characteristics in relation to circulatory arrest in patients with induced circulatory arrest.
- 2) To construct a PPG-based algorithm for detection of circulatory arrest based on induced circulatory arrest data in patients.
- 3) To study the performance (sensitivity and false positive alarms) of the developed PPG-based algorithm for detection of circulatory arrest in patients with induced circulatory arrests.

Secondary Objective(s):

- To study the positive predictive value of the developed algorithm for circulatory arrest detection.
- To study the specificity of the developed circulatory arrest detection algorithm.
  
- To identify potential sources of false positive alarms for circulatory arrests.
- To study PPG signal characteristics in relation to hemodynamically stable cardiac arrhythmias.
- To study PPG signal characteristics in relation to hemodynamically unstable cardiac arrhythmias.
- To study PPG signal characteristics prior to and after TAVR procedure to assess the impact of aortic stenosis and/or regurgitation on the PPG signal.
- To study PPG signal characteristics in patients with and without systemic hypertension.
- To study PPG signal characteristics in relation to left ventricular ejection fraction in patients without relevant valvular lesions.

### 3. STUDY DESIGN

[figure not shown]
The DETECT-1 is a Dutch prospective multicenter observational cohort study performed in a hospital setting. Included patients are hospitalized for ICD implantation, VT ablation or TAVR procedure.

Expected study duration is 2 years.

Data of induced circulatory arrests will be collected in the following settings/patients:

- Patients who undergo ventricular fibrillation induction during defibrillation testing after (subcutaneous) ICD implantation. This is performed as routine practice to test the ability of the implanted device to sense, detect and terminate ventricular fibrillation cardiac arrest appropriately.
- As part of TAVR procedure, rapid ventricular pacing is performed during valve deployment resulting in short-lasting circulatory arrest.
- During ventricular tachycardia (VT) ablation procedure, hemodynamically unstable VT/VF is induced in about 1/3.

Flowchart:

## 4. STUDY POPULATION

### 4.1 Population (base)

The study population will consist of hospitalized patients who undergo short-lasting circulatory arrest induction as part of routine practice during some invasive procedures.

### 4.2 Inclusion criteria

In order to be eligible to participate in this study, a subject must meet one of the following criteria:

- Planned to undergo ventricular fibrillation induction during defibrillation testing after ICD implantation
- Undergoing TAVR procedure with intended rapid ventricular pacing
- Undergoing ventricular tachycardia ablation

Additionally, a subject must meet all of the following criteria:

- Age => 18 years
- Fitting the wristband

### 4.3 Exclusion criteria

A potential subject who meets any of the following criteria will be excluded from participation in this study:

- Unwilling or unable to provide informed consent
- Known hemodynamically relevant subclavian artery stenosis
- Medical issues that interfere with wearing of the wristband (e.g. skin disorders)
- Unavailability of wristband used for PPG recording

### 4.4 Sample size calculation

Targeting a desired sensitivity of 95%, 200 true events allow estimation of sensitivity with precision (expressed as expected width of the 95% confidence interval) of +/- 3%, which is considered adequate. As for specificity, a substantially larger number of “non-events” can be sampled, precision for estimating specificity will be larger.

In this study, we will primarily collect data of induced circulatory arrest, obtained during controlled settings with appropriate reference standards (ECG and (invasive) blood pressure measurements). To collect a sufficient amount of PPG data with true events, the

sample size will be 276 patients consisting of an estimated number of n=200 TAVR-patients (event rate 1/1), n=20 ICD-patients (event rate 1/1) and n=56 VT-ablation patients (event rate 1/3). In case ventricular fibrillation induction or rapid ventricular pacing is not performed or does not result in complete circulatory arrest (as determined on (invasive) blood pressure measurements), the number of patients included will be increased to guarantee the anticipated number of true events, with a maximum of 80 additional patients. Data of the patients without induced circulatory arrest will be used as non-cardiac arrest data.

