## 10. STATISTICAL ANALYSIS

Categorical data will be presented as numbers (percentages) and compared using Chi-square test or Fisher's exact test. Continuous data will be assessed for normal distribution and presented as means  $\pm$  standard deviations or medians (interquartile ranges) whichever appropriate. Comparisons will be performed using the Student's t-test or Mann-Whitney U test, whichever appropriate.

For each patient studied, circulatory arrest data (case data) and non-circulatory arrest data (control data) will be collected. The data obtained will be analysed and used for algorithm development at regular intervals: after inclusion of the first 50 patients with at least one circulatory arrest and afterwards after inclusions of another 50 patients. This enables improvement and refinement of the initial algorithm to gain optimal performance. The first iteration provides a first version of the diagnostic algorithm. The second and third iteration will be used to optimize the algorithm. The fourth iteration will be used as final evaluation of the performance of the algorithm (internal validation). All non-circulatory arrest data will be analyzed for false positive circulatory arrest alarms.

As the algorithm will primarily be developed and validated on non-physiologic circulatory arrest induction using rapid ventricular pacing with aortic balloon inflation during transcatheter aortic valve implantation, a second (external) validation will be performed on data of patients with induced shockable cardiac arrest (i.e. induction of ventricular fibrillation or tachycardias). This most closely resembles clinical sudden cardiac arrest. The final cohort of 50 inclusions with at least one induced event, consisting only of patients who underwent VT ablation or VF induction after s-ICD implantation, will be used for this analysis.

The performance of the PPG-based algorithm will be assessed by calculating the sensitivity, specificity, and positive predictive value with 95% confidence intervals. The specificity is reported based on 1-minute intervals of pulsatile PPG signal correctly identified as non-circulatory arrest. Reporting will follow the recommendations of the STARD guidelines for studies on diagnostic accuracy. Statistical analyses will be performed using SPSS (IBM, Armonk, USA).

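### The ±3-point precision for sensitivity in Section 4.4 rests on 200 evaluated events, but Section 10 evaluates the finished algorithm on sets of 50 event-patients, which give about ±6 points at one event each

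*Protocol*

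**What the plan says.** Sensitivity of the developed algorithm is a primary endpoint, together with false positive alarms (Protocol, Section 8.1.1).

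Section 4.4 bases the sample size on the precision of that sensitivity. It begins "Targeting a desired sensitivity of 95" per cent, states that "200 true events allow estimation of sensitivity with precision (expressed as expected width of the 95% confidence interval) of +/- 3" per cent, and judges this adequate. The planned recruitment is "n=200 TAVR-patients (event rate 1/1), n=20 ICD-patients (event rate 1/1) and n=56 VT-ablation patients (event rate 1/3"), with up to 80 additional patients if inductions are not performed or do not produce a complete arrest.

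Section 10 sets out how the event data will be used. Analysis takes place "after inclusion of the first 50 patients with at least one circulatory arrest and afterwards after inclusions of another 50 patients". Of these batches, "The first iteration provides a first version of the diagnostic algorithm", the second and third refine it, and "The fourth iteration will be used as final evaluation of the performance of the algorithm (internal validation"). A further external validation uses a final cohort of 50 patients with at least one induced event, drawn only from VT ablation and s-ICD testing. Section 10 asks for sensitivity with a 95% confidence interval.

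**The concern.** The two sections use the same 200 event-patients in different ways. Section 4.4 counts all of their events towards estimating sensitivity. Section 10 gives about three quarters of the patients to development and keeps one quarter for the final evaluation. The external cohort is analysed separately and is also planned at 50. The precision that 4.4 calls adequate is therefore not the precision of any evaluation that Section 10 describes.

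This matters because precision is the only justification given for the sample size, and it concerns a primary endpoint. A reader who relies on ±3 points would take an observed 95% as placing sensitivity above about 91%. An evaluation on 50 events cannot do that. The mismatch also creates a temptation to pool the development batches at the end to recover 200 events. That would attach a narrow interval to an estimate made largely on the data that shaped the algorithm, and such an estimate tends to be optimistic.

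**Working it through.** **Inputs.** Target sensitivity p = 0.95, 200 true events, 95% confidence level, stated precision ±3%, and planned numbers and event rates by procedure (all Section 4.4). Batches of 50, iterations 1–3 for development, iteration 4 for evaluation, and an external cohort of 50 (all Section 10).

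**Step 1: reproduce the plan's figure.** The Wald half-width is 1.96 × √(p(1 − p)/n).

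- n = 200: 1.96 × √(0.95 × 0.05/200) = 3.02 points. The stated ±3% reproduces. It is a half-width; the full width is about 6.0 points.
- Inverse: 1.96² × 0.0475/0.03² = 202.7, so about 203 evaluated events are needed for ±3.
- Exact (Clopper-Pearson) interval for 190/200: 91.0% to 97.6%.

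**Step 2: count the events left for evaluation.** Development uses 3 × 50 = 150 event-patients. Iteration 4 has 50. The external cohort has 50.

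**Step 3: precision for those sets, at one event per patient.**

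| Set | Events | Wald half-width (points) |
|---|---|---|
| Section 4.4 as stated | 200 | 3.02 |
| Iteration 4 | 50 | 6.04 |
| External cohort as planned | 50 | 6.04 |
| Both pooled (not proposed in the protocol) | 100 | 4.27 |

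At n = 50 the expected half-width is 6.4 points with Wilson intervals and 6.9 with exact intervals. Exact intervals for the results nearest 95% are:

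- 47/50 (94%): 83.5% to 98.7%
- 48/50 (96%): 86.3% to 99.5%

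**Step 4: allow for several events per patient.** Section 10 counts patients with at least one arrest, and the protocol gives no number of events per patient. As an assumption, let m be events per patient and ρ the within-patient correlation of detection. The effective number is 50m/(1 + (m − 1)ρ).

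- m = 2, ρ = 0: 100 events, ±4.27 points.
- m = 4, ρ = 0: 200 events, ±3.02 points.
- As m grows, the effective number cannot exceed 50/ρ. Since 50/203 ≈ 0.25, no number of repeats reaches 203 once ρ is above about 0.25.

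**Step 5: expected size of the external cohort.** If all ICD and VT-ablation patients are kept for it, the planned numbers give 20 × 1 + 56 × 1/3 = 38.7 expected event-patients. The half-width is 1.96 × √(0.0475/38.7) = 6.9 points. The shortfall against 50 is about 11 event-patients, to be met from additional inclusions.

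**The case against.** **There is no arithmetic error in 4.4.** This is correct. The formula and result are sound for 200 evaluated events. The fault is an inconsistency between 4.4 and Section 10.

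**Events are not patients.** The protocol describes the one-in-three figure for VT ablation as the share of patients in whom an unstable rhythm is induced. On that usage, 1/1 means that every patient has an event, not that each has exactly one. Fifty event-patients are therefore a minimum of 50 events. This stands, and it makes ±6 the one-event case. It does not restore ±3, which would need about four independent events per patient, a figure the protocol does not give.

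**The fourth iteration might be evaluated on all 200 patients cumulatively.** Then 150 of the 200 would have built and tuned the algorithm, and ±3 would describe the spread of a probably optimistic estimate. This reading does not rescue the statement.

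**Little depends on the figure.** The study is observational algorithm development. The protocol ties no hypothesis test, success threshold or stopping decision to ±3, and it already requires confidence intervals, so the real precision will be visible in the results. This limits the consequence. It does not make the statement correct, and the point is not a detail left to an analysis plan: the protocol itself states a figure that its own analysis section does not deliver.

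Some stronger readings that a reader might infer are not supported:

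- *An observed 94–96% leaves sensitivity in the low 80s open.* The exact lower limits are 83.5% at 47/50 and 86.3% at 48/50, so at 96% even 85% is excluded.
- *Iteration 4 may hold fewer than 50 event-patients, because only the first batch is expressly tied to an arrest.* The sentence reads naturally as further batches of the same kind. Section 4.4 also adds patients, and Section 8.5 replaces withdrawals, to protect the number of events.
- *Section 4.4 was left behind when Amendment 3 introduced the split.* The amendment log says only that the analysis was detailed and an external validation subgroup added. It does not say that the four iterations were new.
- *Cross-validation over all events would recover ±3.* Section 10 describes sequential refinement and names no fitting procedure that could be repeated within each fold. Optimism from design choices made on earlier batches might remain.

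**Conclusion.** The concern holds as an inconsistency. The ±3-point precision in Section 4.4 is correct for 200 evaluated events, but Section 10 evaluates the finished algorithm on 50 event-patients in iteration 4 and on a separate 50 in the external cohort. At one event per patient and 95% sensitivity, each set gives about ±6 points (6.04 Wald; 6.4 to 6.9 expected with Wilson or exact intervals), twice the stated figure.

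The size depends on the number of arrests per patient, which the protocol does not give. Two independent events each would bring it to about ±4.3, and within-patient correlation would widen that again. For the external cohort, the planned numbers support about 39 expected event-patients, or about ±6.9, unless additional inclusions close the gap to 50.

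The split itself is a strength, because it protects the reported sensitivity from optimism. What is wrong as written is the single precision statement.

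**What to change.** In Section 4.4, replace the single ±3% statement with the precision for each evaluation set, at 95% sensitivity and one event per patient:

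- iteration 4: about ±6 points
- external cohort: about ±6 points with 50 event-patients, or about ±7 if only about 39 accrue

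Add that iterations 1–3 are for development only and are not pooled into the reported sensitivity. If several arrests per patient are expected, give the assumed number and say that within-patient correlation limits the gain.

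The cost is a change of wording. No extra patients or procedures follow from it. The stated precision becomes less favourable, and the sponsor must decide whether about ±6 points is still adequate for this stage of development.

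### Section 4.4 takes the 1/3 rate of haemodynamically unstable VT/VF as the rate of complete arrest in VT ablation; the 200-event target survives, but the VT/s-ICD external validation cohort loses yield and the top-up trigger does not cover it

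*Protocol*

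**What the plan says.** Section 4.4 builds the sample size from three groups. The "sample size will be 276 patients consisting of an estimated number of n=200 TAVR-patients (event rate 1/1"), with "n=20 ICD-patients (event rate 1/1") and "n=56 VT-ablation patients (event rate 1/3"). Its precision statement is "Targeting a desired sensitivity of 95%, 200 true events allow estimation of sensitivity with precision" of plus or minus 3%.

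The only source for the 1/3 is Section 3, repeated in Section 8.3.2 (VT ablation): "hemodynamically unstable VT/VF is induced in about 1/3". Section 8.3.2 then says that arrest in these patients is confirmed on invasive pressure and ECG, with the arterial line serving to show that the arrest is complete.

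The top-up rule in 4.4 begins "In case ventricular fibrillation induction or rapid ventricular pacing is not performed or does not result in complete circulatory arrest", judged on blood pressure. It then allows up to 80 additional patients, so that the anticipated number of true events is reached. VT ablation is not named in that trigger.

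Section 2 has a secondary objective on the unstable state itself: "To study PPG signal characteristics in relation to hemodynamically unstable cardiac arrhythmias". Section 10 reserves a final cohort of 50 patients with at least one induced event, drawn only from VT ablation and s-ICD testing, for external validation.

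**The concern.** The planning rate and the counting rule refer to different events. A haemodynamically unstable VT may keep some output, and such an induction does not meet the complete-arrest standard. Using 1/3 as the true-event rate treats every unstable VT/VF as a complete arrest, and the protocol gives no figure to support that.

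At stake is the part of the study that rests on these patients. Section 10 justifies the external validation cohort on the ground that induced VF or VT is closer to clinical sudden cardiac arrest than rapid pacing during TAVR. If the VT-ablation yield is lower than planned, this is the cohort that suffers. As worded, the top-up rule reacts to failed VF induction or failed rapid pacing but not to a VT ablation that yields no complete arrest.

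**Working it through.** **Inputs.** From 4.4: 200 TAVR at 1/1, 20 ICD at 1/1, 56 VT ablation at 1/3, target 200 events, sensitivity 95%, at most 80 extra patients. From Section 10: 50 VT-ablation or s-ICD patients with an event. Assumed: c, the share of patients with an induced unstable VT/VF in whom it is a complete arrest. The protocol gives no value for c; 0.5 to 1 is shown for illustration.

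**The plan's own figures.**
- 200 + 20 + 56 = 276, as stated.
- Half-width = 1.96 × √(0.95 × 0.05 / n). For n = 200 this is 3.02 points, and exactly 3 points needs 203 events. The plus or minus 3% reproduces.
- Yield implied by the stated rates: 200 + 20 + 56/3 = 238.7 patients with an event.

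**Yield when complete arrest is counted.** VT-ablation yield = 56 × (1/3) × c.

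| c | VT ablation | ICD + VT | All groups | Short of 50 | Half-width, ICD + VT (points) |
|---|---|---|---|---|---|
| 1 | 18.7 | 38.7 | 238.7 | 11.3 | 6.9 |
| 0.75 | 14.0 | 34.0 | 234.0 | 16.0 | 7.3 |
| 0.5 | 9.3 | 29.3 | 229.3 | 20.7 | 7.9 |

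The half-widths use the formula above at 95% sensitivity, with one event per patient. They are approximate at such small n. A full cohort of 50 would give 6.0 points.

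**Overall target.** At c = 0, 200 + 20 = 220 events remain, with a half-width of 2.9 points.

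**What would fill the cohort of 50.** With 20 ICD events, 30 must come from VT ablation, which needs 30 / (c/3) = 90/c patients: 90 at c = 1, 120 at c = 0.75 and 180 at c = 0.5, against 56 planned. If all 80 extra places went to VT ablation, 56 + 80 = 136 patients would give 136/3 × c = 45.3c events. That reaches 30 in expectation only if c is at least 30/45.3, about 0.66.

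**The top-up trigger.** In the inclusion criteria (4.2), VF induction is the ICD-testing criterion, rapid pacing the TAVR criterion, and VT ablation a third, separate one. The trigger in 4.4 uses the first two terms only.

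**The case against.** The strongest reply is that no figure stated in 4.4 fails. That is right: 276 and plus or minus 3% both reproduce, and the 200-event target holds with no VT-ablation event at all. A reader might infer from the mismatch that the main precision claim is in danger, and the numbers do not support that. A reader might also say that the protocol overstates its precision in VT/VF patients. It states none, so the half-widths above describe what the design delivers and correct no figure in the protocol.

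The cohort of 50 is short by 11.3 even at c = 1. That part does not come from the meaning of 1/3; only the further loss as c falls below 1 does.

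The two event concepts are also not cleanly separated in the text. Section 3 lists VT ablation among the settings for induced circulatory arrest data, and Section 10 describes the external validation events as induced VF or tachycardias. This is a reason to reconcile the definitions. It does not supply the missing rate of complete arrest, and 4.4 and 8.3.2 still apply the stricter standard.

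The 18.7 is an upper limit only on expected patients with an event, and only at a rate of exactly 1/3. The source says about 1/3, and one patient may contribute several events. Nor is VT ablation the only group with an uncertain yield: the top-up rule exists because rapid pacing in TAVR may be omitted or fail.

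On the trigger, one can argue that VT-ablation non-events are already priced into the 1/3, so they need no replacement, and that VF arising during an ablation falls under the wording. Both points stand in part. The first covers patients without an unstable arrhythmia but not unstable inductions that fall short of arrest. The second does not reach VT. It would go too far to say that extra patients cannot be VT-ablation patients: the rule omits them from its trigger but does not say from which group the 80 come.

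**Conclusion.** The point holds in a limited form. The VT-ablation rate in 4.4 belongs to a broader event than the one counted, so 18.7 is the most that can be expected at the stated rate; with c between 0.5 and 1 it is 9.3 to 18.7. ICD plus VT ablation then gives 29.3 to 38.7 patients with an event against the 50 in Section 10. Up to 9.3 of the shortfall (38.7 − 29.3) comes from c over that range, and 11.3 is there regardless. The overall 200-event target stands. The result rests on the stated rates, one event per patient, and a value of c that the protocol does not give. It merits correction because the cohort affected is the one that Section 10 regards as closest to clinical cardiac arrest, and the correction is cheap.

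**What to change.** 1. In 4.4, label 1/3 as the rate of haemodynamically unstable VT/VF.
2. State the expected number of complete arrests in VT ablation as 56/3 × c. Take c from the VT-ablation patients already recorded, or give an openly assumed range.
3. Reconcile what counts as an event across Sections 3, 4.4, 8.3 and 10.
4. Extend the top-up trigger to a shortfall in confirmed VT/VF events against the number needed for the external validation cohort, within the existing maximum of 80. Do not make every VT-ablation patient without an arrest a trigger: even at c = 1, 56 − 18.7 = 37.3 of the 56 are planned non-events, and replacing them would use nearly half of the 80 places.
5. If the cohort still cannot be filled, give its expected size and precision in Section 10: about 6.9 points either side at 38.7 events and 7.9 at 29.3, for a sensitivity of 95%.

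The cost is a paragraph in 4.4 and matching wording in the other sections. The yield implied by 4.4 becomes less favourable, and some top-up places are directed to ICD and VT-ablation patients. The cap on additional patients is unchanged.
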